7.2 Analysis of Correlative Endpoints

The analyses of pre- and post-treatment PB and BM specimens for immune parameters will be descriptive and graphical in nature. Data will be summarized for each cohort separately. The change in flow values at each time point after Idelalisib relative to the baseline value will be checked for skewness and log-transformed as appropriate. The changes will be modeled using mixed-effects, linear regression models that included fixed effects for time and a random effect for the patient to account for within-patient correlation of measurements. To explore potential differences in the change in flow values across patient subgroups, interaction terms will be included in the regression models. Post-treatment changes in gene expression in immune gene signaling circuits in tumor biopsies and PB will be summarized with descriptive statistics and correlated with clinical outcomes.

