4.3. TABLE 1. SCHEDULE OF ASSESSMENTS

	Screening and Baseline ()	Cycle 1, Day 1 Day +90 (± 10 Days)) Cycle 1, Day 15	(± 7 Days) Cycles 2-6, Day 1	30 days Post last dose	Month 12 (± 14 Days)
Informed Consent ^a	Days 60 -100					
Medical History	X					
Physical Exam	X	X		X	X	X
AE Assessment	X	X		X	X	X
CBC with diff	X	X	X	X	X	X
Comprehensive metabolic panel e (CMP) ^b	X ^b	X ^b	X ^b	X ^b	X ^b	X ^b
PT, PTT, INR	X					
Serum β -HCG (if applicable)	X					
CMV PCR ^d	X ^d	X	X	X		
Dispense Idelalisib		X		X		
Standard of care per institution						
T-cell chimerism	X					X
Bone marrow biopsy (as std of care)	X					X
aGVHD/cGVHD assessments	X	X	X	X		X
Correlative studies ^c	X	X		X ^c		X

^aInformed consent will be collected beginning on Day +60 after BMT until Day +100.

^b CMP to include BUN, creatinine, sodium, potassium, chloride, AST, ALT, total bilirubin, alkaline phosphatase.

^c Additionally specimens should be obtained from peripheral blood and bone marrow collections as a part of routine clinical care such as GVHD, toxicity and/or disease relapse Correlative peripheral blood samples should be collected on Day 1 of every other cycle beginning with Cycle 2

^d Cytomegalovirus (CMV) viral load assay will be monitored by PCR every 14 days between days +90-and day +120, then monthly through day +270: treat according to BMT policy guidelines.

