6. STUDY STATISTICS

This is a phase I study of Idelalisib, an orally-administered, selective inhibitor of Phosphoinositide 3 kinase (PI3K)- δ . It has been successfully used pre-transplant to induce partial and complete responses in many B-cell derived malignancies. In this study Idelalisib will be evaluated in the post-transplant setting. Patients receiving a standard of care allogeneic hematopoietic stem cell transplant from any source: cord, marrow, or peripheral blood will be eligible. Patients will be randomized in a 2:1 ratio to either 100 mg Idelalisib twice daily from day 90 (\pm 10 days) following transplant, Arm A, or a placebo, Arm B, and monitored for toxicity until day 270.

Study treatment plan: Idelalisib day +90 [+/- 10 days), 100mg twice daily, and at least 5 days after the discontinuation of filgrastim if ANC is greater than 1,000 and PLT 50>Gi/L and <grade 2 aGVHD. Patient's Idelalisib will be dose adjusted for the expected toxicities of Idelalisib including pneumonitis, hepatitis, neutropenia, thrombocytopenia and loose stools.

Primary endpoint and design: The primary goal of this study is to evaluate the safety of Idelalisib as post-transplantation maintenance in patients undergoing an allogeneic BMT. In addition to the allowed dose reductions, a safety monitoring plan will be implemented to ensure that other treatment-limiting events are not elevated. The study will be monitored between the date of randomization and day 270 post-transplant. For safety monitoring, treatment-limiting toxicities will be defined as Idelalisib interruption for >14 days, or other grade 3 or higher adverse events as defined by CTCAE IV not captured in the protocol for dose de-escalation. The trial will assume that, *a priori*, the probability of these events in both arms of the study will follow a Beta (0.10, 0.90) prior distribution. This distribution corresponds to an assumption that 10% of patients might experience a treatment-limiting toxicity.

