7. CORRELATIVE STUDIES

7.1 RATIONALE AND OUTLINE OF CORRELATIVE STUDIES

The overarching goals of our correlative studies are to:

- i) Characterize the effect of Idelalisib on allogeneic T and B cells, particularly on their re-distribution, in vivo expansion, activation, and effector differentiation after treatment
- ii) Identify potential predictive biomarker candidates to allow for better selection of patients after alloBMT who may benefit or whom are likely to have toxicity from Idelalisib therapy.
- iii) Characterize the mechanisms of relapse after Idelalisib such as B cell and T cell dysfunction.

Hypothesis: We hypothesize that Idelalisib administration will have an effect on GVHD modulation. This prediction is based on the data suggesting that PI3K pathway is activated in activated/memory T cells responsible for autoimmunity (16). Interestingly, Ali et al., have recently shown that PI3K α inactivation results in the disruption of two tumor-associated immune-suppressive cell types- regulatory T cells and myeloid-derived suppressor cells (17). Thus, we also hypothesize that p110 α inhibition with Idelalisib can enhance allogeneic antitumor immunity post-transplant that can be measured as increased TCR diversity and the emergence of unique TCR clonotypes.

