Flow Cytometry Studies: We will perform multi-color flow cytometry on peripheral blood (PB) and bone marrow (BM) specimens before and after Idelalisib treatment using three pre-determined panels of mAbs including but not limited to those specific for CD3, CD4, CD8, PD-1, CD45RA, CCR7, CD25, CD27, CD28, CD69, Ki-67, T-bet, CD127, FoxP3, HLA-DR, CTLA-4, TNFR11, TIM3, LAG-3, CD160, 2B4, BTLA, KLRG-1, CD16, and CD56. This multi-color approach allows examination of different CD4+ and CD8+ T cell subpopulations (expressing CD45RA, CCR7, CD27, and CD28), phenotypic separation of human CD4+FoxP3+ T cells into three distinct subpopulations as well as assessment of their proliferative status (% Ki-67 positive cells). (18) The expression of CD69, HLA-DR and TNFR11 will be measured to characterize T cells activation status and the expression of co-inhibitory molecules (PD-1, TIM3, LAG-3, CD160, 2B4, BTLA, KLRG-1) will be studied. Natural killer cells (NK), NK-T cells will be enumerated using CD16 and CD56 (NK/NK-T cells). Additionally effects of Idelalisib on myeloid-derived suppressor cells and B cell depletion post-transplant will be assessed. As a part of PBMCs collection and mononuclear cell isolation we will also collect plasma that will be stored and used for measurement of defined cytokines (IL-2, IL-6, IL-10, IFN- γ , TNF- α) to assess Idelalisib -induced global T cell activation or for proteomic analysis of defined molecules associated with GVHD (proteomic studies on PTCy-based platforms are being prepared for publication (20)).

Molecular studies: Immune Profiling of T cell Repertoire: The studies proposed will evaluate the T cell receptor (TCR) diversity in T cells isolated from PB and BM from patients before and after treatment with Idelalisib on the parent clinical trial. We will determine TCR diversity and clonal composition using a molecular

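### For the flow-cytometry markers, the Section 7.2 model names time and patient effects but no arm term, so the plan does not commit to estimating the randomized idelalisib–placebo difference

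*Combined protocol and SAP*

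**What the plan says.** Section 7.2 takes as outcome the change in flow values from baseline after idelalisib, log-transformed where skewed. The models are "mixed-effects, linear regression models that included fixed effects for time and a random effect for the patient to account for within-patient correlation". Arm, placebo and arm-by-time are not mentioned.

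Two other sentences in Section 7.2 come near an arm comparison:

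- "Data will be summarized for each cohort separately". Section 7 does not define cohort.
- "To explore potential differences in the change in flow values across patient subgroups, interaction terms will be included in the regression models". No subgroup is named.

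The section describes the immune-parameter analyses as "descriptive and graphical in nature", and Section 2.3 places them among the tertiary endpoints.

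The first correlative goal in Section 7.1 is to "Characterize the effect of Idelalisib on allogeneic T and B cells". On design, Section 6 states: "Patients will be randomized in a 2:1 ratio to either 100 mg Idelalisib twice daily", the alternative being placebo, with 30 patients in Arm A and 15 in Arm B.

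On sampling, the footnote to Table 1 in Section 4.3 says: "Correlative peripheral blood samples should be collected on Day 1 of every other cycle beginning with Cycle 2". It limits this to neither arm. Section 7.1, however, describes flow cytometry on specimens taken "before and after Idelalisib treatment using three pre-determined panels of mAbs", and does not mention placebo specimens.

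**The concern.** The goal is a drug effect, and the trial has a randomized placebo arm that can isolate it. From about day +90 after transplant, blood and immune values may move without any study drug. Section 5.1 itself notes that late neutropenia is common in these patients after neutrophil recovery. A model with time but no arm cannot separate that shared movement from the effect of idelalisib. A marker that rises equally in both arms could then be reported as a change after idelalisib.

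What is at stake is the reading of the flow-marker results. They are meant to show what idelalisib does to T and B cells and to inform later biomarker work.

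**Working it through.** The plan gives no figure for this analysis, so there is none to reproduce. The check asks what each possible fit estimates, and then how precise the missing contrast would be.

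**Inputs.** From the documents: 30 v 15 patients (Section 6); correlative blood on Day 1 of every other cycle from Cycle 2 within Cycles 2–6, hence Cycles 2, 4 and 6 (Section 4.3); 25 named antibodies, a list stated to be open (Section 7.1). Assumed, because the documents give no values: shared change S of 0 to 0.5 SD, drug effect D of 0 or 0.5 SD, where SD is that of the change score.

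**What each fit estimates at a visit.** Mean change is S in Arm B and S + D in Arm A.

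- Arm A alone: S + D.
- Arms pooled: [30(S + D) + 15S]/45 = S + 0.667D.
- Separate fit by arm: S and S + D side by side, with no stated difference or interval.
- Arm contrast: (S + D) − S = D.

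| Quantity, S from 0 to 0.5 SD | D = 0 | D = 0.5 SD |
|---|---|---|
| Arm A alone | 0 to 0.50 | 0.50 to 1.00 |
| Arms pooled | 0 to 0.50 | 0.33 to 0.83 |
| Arm contrast | 0 | 0.50 |

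These are visit-specific mean changes, not necessarily single time coefficients. With an intercept and a reference visit, a change that is constant across visits sits in the intercept. With continuous time the coefficient is a slope. Section 7.2 does not state the coding.

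**Simulation check.** The set-up was 30 v 15 patients, four post-baseline visits, between-patient and residual SD 0.7 each (assumed), and 60 runs per scenario. Values are at the last visit.

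| Shared change, drug effect | Pooled, time only | Arm A mean | Arm contrast |
|---|---|---|---|
| 1.0, 0 | 0.99 | 0.99 | 0.01 |
| 0, 0.75 | 0.49 | 0.75 | 0.78 |
| 0.5, 0.75 | 1.01 | 1.26 | 0.75 |

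The formulas give 1.0, 1.0, 0; then 0.50, 0.75, 0.75; then 1.00, 1.25, 0.75. The agreement is within simulation error.

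**Precision of the contrast at one visit.** SE = sqrt(1/nA + 1/nB) and half-width = t(0.975, nA + nB − 2) × SE. The detectable difference is for 80% power, two-sided 0.05, by the noncentral t. The missing-sample rates are assumptions.

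| Patients sampled | SE (SD) | 95% half-width (SD) | Detectable at 80% power (SD) |
|---|---|---|---|
| 30 v 15 (all) | 0.316 | 0.638 | 0.906 |
| 24 v 12 (20% missing) | 0.354 | 0.719 | 1.020 |
| 20 v 10 (33% missing) | 0.387 | 0.793 | 1.124 |

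**Average of three visits, 30 v 15.** SE = 0.316 × sqrt((1 + 2r)/3). For assumed within-patient correlation r = 0.3, 0.5 and 0.7, SE is 0.231, 0.258 and 0.283, and the half-width is 0.466, 0.521 and 0.570 SD.

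**Multiplicity, as an example only.** If each of the 25 antibodies were one endpoint, 25 × 3 = 75 contrasts. With no true effects, 75 × 0.05 = 3.75 intervals would be expected to exclude zero. With one average per marker it is 25 × 0.05 = 1.25. Several antibodies are used jointly to define cell subsets, so the true number of endpoints is not known from the documents.

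**The case against.** The strongest reply is that the plan may already contain the comparison. In a two-arm trial, cohort plausibly means arm. If the model is also fitted by arm, placebo shows the shared change, idelalisib shows the shared change plus the drug effect, and a reader can subtract. Time is the only fixed effect named, so the subgroup interactions would naturally be subgroup-by-time, and arm is an obvious candidate. The analyses are also declared descriptive, and Section 2.1 ties the placebo comparison to safety.

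Much of this stands. A reader might infer that arm is ruled out of the model, or that the reported changes will be confounded. The text supports neither: arm is unspecified, and under separate fits by arm nothing is confounded. A reader might also infer that the plan never compares the arms, but Section 6 compares them for treatment-limiting toxicity. Nor do the documents show that placebo patients go unsampled. The schedule has no arm restriction, and the before-and-after-idelalisib wording in Section 7.1 leaves the matter open.

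What does not stand is that the gap is therefore closed. Neither term is defined, and neither sentence commits to the between-arm difference. Separate summaries give no interval for that difference. A descriptive purpose does not settle the matter either: the plan does commit to a regression model, and an exploratory estimate with an interval is compatible with description.

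**Conclusion.** The point holds as a minor one, limited to the flow-cytometry markers. It is certain that Section 7.2 names no arm or arm-by-time term and that no other section commits to an idelalisib–placebo estimate for these markers.

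The consequence depends on how the model is fitted. With Arm A alone, the reported change exceeds the drug effect by the whole shared change. With the arms pooled, it contains the shared change and only about two-thirds of the drug effect. With separate fits by arm, only the difference and its interval are missing. The two-thirds follows from the 2:1 allocation; the 0 to 0.5 SD range for shared change and the 0.5 SD drug effect are illustrative assumptions.

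It would be wrong to read this as a threat to the trial's main conclusions: primary safety and one-year event-free survival do not use this model.

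**What to change.** In Section 7.2:

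1. Define cohort as randomized arm.
2. Fit scheduled peripheral-blood flow values from both arms in one model with time (as visits), arm and arm-by-time, and baseline value as an optional covariate.
3. Report the between-arm difference in mean change with a 95% interval for Cycles 2, 4 and 6, by visit or as one average per marker. Report month 12 separately, because dosing ends at day +270; if month 12 is counted from transplant, that sample falls about 365 − 270 = 95 days later.
4. Analyse bone marrow separately, and keep samples triggered by GVHD, toxicity or relapse out of this model, because their timing depends on outcome.
5. Label the estimates exploratory and unadjusted for multiplicity.
6. Confirm that placebo patients are sampled on the same schedule.

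The cost is a few sentences, and no new specimens if placebo patients are already sampled. There are two downsides. The estimates will be imprecise, so the intervals should be read as estimates and not as powered tests. There will also be many unadjusted contrasts, some of which will exclude zero by chance; one average per marker reduces their number.

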2.3. TERTIARY ENDPOINTS

To explore the association between potential biomarkers, clinical activity and/or toxicity of Idelalisib administered after allogeneic BMT. Multi-color flow cytometric analyses of immune markers pre- and post-treatment, high-throughput DNA sequencing of rearranged TCR β CDR3 regions from T cell genomic DNA, cytokine measurements, and immunohistochemistry is planned. In addition, we may perform exploratory gene expression analysis of immune biomarkers in the bone marrow aspirates and whole or targeted exome sequencing of the lymphoma cells.

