7.3 OPERATING PROCEDURES FOR SPECIMEN COLLECTION

Peripheral blood and bone marrow specimen collection will be performed as delineated in the Table 1 Schedule of Assessment Section 4.3 and additionally at the times when peripheral blood and bone marrow collections are performed for clinical care such as GVHD, toxicity and/or disease relapse.

Bone marrow: 4 x 8mL will be collected in green top sodium heparin tubes (~20-30 mL). Re-adjustment of the direction of bone marrow aspirate needle should take a place after each 10 cc is collected to prevent hemodilution. At the time of collection, green top tubes must be thoroughly mixed to prevent clotting.

Peripheral blood: 5x8mL green top sodium heparin tubes of blood (~40mLs) will be collected at each time point.

Specimens should be labeled with the patient's study number (given at the time of registration), study number, sample collection date and time, and sample source (PB or BM). Sample collection date and time, and sample source (PB or BM) will be recorded on correlative collection worksheet and copy included with delivery. All data should be kept in laboratory log. At each sampling time, BM and PB mononuclear cells (PBMC) will be processed via Ficoll density gradient centrifugation. The washed cells will be counted, triaged for DNA isolation, and viably cryopreserved using a controlled-rate freezer with transfer to the vapor phase of liquid nitrogen for long-term storage ([name] laboratory).

The Sidney Kimmel Comprehensive Cancer Center (SKCCC) specimens should be delivered to the [name] laboratory immediately after collection.

[figure not shown]
Specimen collection / processing: PB and BM specimens should be collected as outlined in the Trial Flow Chart 6.0.

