Appendix 2: Study Calendar and Schema

12.1. STUDY CALENDAR

	Screening and Baseline ()	Cycle 1, Day 1 Day +90 (± 10 Days)	Cycle 1, Day 15	Cycles 2-6 Day 1 (+/- 7 days)	30 days Post last dose	Month 12 (± 14 Days)
Informed Consent ^a	Days 60 -100					
Medical History	X					
Physical Exam	X	X		X	X	X
AE Assessment	X	X		X	X	X
CBC with diff	X	X	X	X	X	X
Comprehensive metabolic panel e (CMP) ^b	X ^b	X ^b	X ^b	X ^b	X ^b	X ^b
PT, PTT, INR	X					
Serum β-HCG (if applicable)	X					
CMV PCR ^d	X ^d	X	X	X		
Idelalisib		X		X		
Standard of care per institution						
T-cell chimerism	X					X
Bone marrow biopsy (as std of care)	X					X
aGVHD/cGVHD assessments	X	X	X	X		X
Correlative studies ^c	X	X		X ^c		X

^aInformed consent will be collected beginning on Day +60 after BMT until Day +100.

^bCMP to include BUN, creatinine, sodium, potassium, chloride, AST, ALT, total bilirubin, alkaline phosphatase.

^c Additionally specimens should be obtained from peripheral blood and bone marrow collections as a part of routine clinical care such as GVHD, toxicity and/or disease relapse Correlative peripheral blood samples should be collected on Day 1 of every other cycle beginning with Cycle 2

^dCytomegalovirus (CMV) viral load assay will be monitored by PCR every 14 days between days +90-and day +120, then monthly through day +270: treat according to BMT policy guidelines.

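### Section 7.2 analyses tumor biopsies that no visible schedule collects, its only scheduled post-baseline marrow is off drug, and its model has no arm term to separate idelalisib from transplant recovery

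*Combined protocol and SAP*

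**What the plan says.** Section 7.2 contains three relevant statements.

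- On gene expression: "Post-treatment changes in gene expression in immune gene signaling circuits in tumor biopsies and PB will be summarized with descriptive statistics". These changes are also to be correlated with clinical outcomes.
- On immune parameters: "The analyses of pre- and post-treatment PB and BM specimens for immune parameters will be descriptive and graphical in nature".
- On flow values: change from baseline at each time point is modelled with time as a fixed effect and a patient-level random effect. Interactions are added for patient subgroups that are not named, and summaries are given by cohort, a term the section does not define.

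Section 2.3 describes the tissue work as optional and as "exploratory gene expression analysis of immune biomarkers in the bone marrow aspirates". It also mentions exome sequencing of lymphoma cells, without naming the specimen.

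On collection, Section 7.3 states: "Peripheral blood and bone marrow specimen collection will be performed as delineated in the Table 1 Schedule of Assessment Section 4.3". It adds samples "additionally at the times when peripheral blood and bone marrow collections are performed for clinical care such as GVHD, toxicity and/or disease relapse". The calendars in Section 4.3 and Appendix 2 (Section 12.1) have a row "Bone marrow biopsy (as std of care"), marked at Screening/Baseline and Month 12 only. Footnote c limits the every-other-cycle correlative samples, starting at Cycle 2, to peripheral blood.

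**The concern.** There are three separate problems.

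1. **Specimen.** The analysis section names a tissue that the collection sections do not provide and that differs from the tissue named in Section 2.3.
2. **Timing.** Dosing is planned to end at day +270 and the second scheduled marrow comes later. A marrow change could be read as an on-treatment drug effect when the sample was taken off drug.
3. **Attribution.** Patients are rebuilding an immune system from a new donor throughout the study. A model with time but no arm describes how flow values move after transplant; it does not isolate what idelalisib adds.

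The first goal in Section 7.1 is to characterize the effect of idelalisib on donor T and B cells. Ordinary reconstitution could be reported as that effect, or a real effect could be lost within it, although the trial has a randomized placebo arm that can separate the two.

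**Working it through.** **Specimen, sections side by side.**

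| Place | Tissue named |
|---|---|
| Section 7.2, gene expression | tumor biopsies and blood |
| Section 2.3 | bone marrow aspirates (optional) |
| Section 4.3 and Appendix 2 calendars | blood and marrow; no tumor-biopsy row |
| Section 7.3, collection | blood and marrow; source recorded as blood or marrow only |
| Section 7.3, freezing protocol label | blood or marrow |

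Scheduled tumor biopsies in the visible text: 0.

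**Timing.** Inputs: start about day +90 for 180 days (Introduction); treatment through day +270 (Section 4); start window ±10 days; Month 12 window ±14 days.

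- Planned last dose: 90 + 180 = day 270, which reproduces the protocol's figure.
- Month 12 counted from transplant (assumption: day 365): 365 − 270 = 95 days off drug. With the visit window: 351 − 270 = 81 to 379 − 270 = 109.
- If the start window also shifts a full 180 days of dosing (last dose day 260 to 280): 351 − 280 = 71 to 379 − 260 = 119.
- Month 12 counted from first dose (day 90 + 365 = 455): 455 − 270 = 185 days. With the visit window: 441 − 270 = 171 to 469 − 270 = 199.
- Interval from baseline to Month 12 marrow, counted from transplant, taking the day 60 to 100 consent window as the baseline window (assumption): 351 − 100 = 251 to 379 − 60 = 319 days of recovery.

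Scheduled on-drug marrow after baseline: 0. Scheduled on-drug correlative blood after Cycle 1 Day 1: 3, at Cycles 2, 4 and 6. With 30-day cycles, which give 6 × 30 = 180 days, these fall on days 120, 180 and 240.

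**Attribution.** Let R be the mean change from baseline due to post-transplant recovery, the same in both arms in expectation under randomization, and D the extra change due to idelalisib at a given time point. Arm A changes by R + D and Arm B by R.

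- Time-only model, both arms, Section 6 sizes of 30 and 15: [30(R + D) + 15R] / 45 = R + (2/3)D.
- Time-only model in Arm A alone: R + D.
- Arm A minus Arm B: (R + D) − R = D.

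Only the last removes R. With D = 0, the first two still return R. The documents give no figure for R, so the size of the bias is unknown. It applies to blood as well as marrow.

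**Precision of the arm contrast.** Assuming a common standard deviation s of the change and a sample from every patient, the standard error is s√(1/30 + 1/15) = s√0.10 = 0.316s. The approximate 95% half-width is 1.96 × 0.316s = 0.62s. It is wider if standard-of-care marrow is not obtained in everyone.

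**The case against.** A good deal can be said for the plan.

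- **Section 7.2 promises a pre- and post-treatment comparison, not on-drug marrow.** Screening and Month 12 marrow supply it. This stands: a reader might infer that the marrow correlatives cannot measure what Section 7.2 analyses, and the text does not support that.
- **Marrow drawn for GVHD, toxicity or relapse may fall during dosing and may contain tumor.** This also stands, so it would be wrong to say that on-drug marrow is impossible or that there will be no tumor material. Such samples are selected by events and do not form a paired series.
- **Nothing states that Month 12 is pooled with Cycles 2, 4 and 6.** Correct: Section 7.2 looks at each time point. What is missing is a label separating on-drug from off-drug time points.
- **The placebo arm handles recovery.** It can, and a Month 12 difference between arms could show a persisting effect. However, the model names no arm term. If cohort means arm, separate summaries still give no contrast. If arm is one of the unnamed subgroups, the text should say so.
- **Material may be missing.** Section 7.3 refers to a trial flow chart next to a figure that is not reproduced. The statement about tumor biopsies therefore covers the visible text only.

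**Conclusion.** The point holds in a limited form. Section 7.2 names tumor biopsies that no visible section collects, and it disagrees with Section 2.3. Scheduled post-baseline marrow is a single standard-of-care sample, about 95 days after the planned last dose (81 to 109) if Month 12 runs from transplant, or about 185 days (171 to 199) if it runs from first dose. Neither gap should be quoted as the protocol's own figure, because the anchor is not stated; both put the sample well off drug for a patient who completes dosing on schedule. The flow-value model, as written, cannot separate an idelalisib effect from immune recovery.

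The timing point does not touch the Cycle 2, 4 and 6 blood samples, which are scheduled during dosing. The missing arm term affects them too. The gene-expression summaries are descriptive and lie outside the mixed model, so for them the issues are the specimen name and the lack of a stated arm comparison. All of this is tertiary and exploratory. The primary safety endpoint, the sample size of 45 and the safety monitoring rule are unaffected.

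**What to change.** 1. In Section 7.2, replace tumor biopsies with bone marrow aspirates, to agree with Sections 2.3 and 7.3.
2. Add arm and arm-by-time terms to the mixed model, and report idelalisib effects as Arm A versus Arm B contrasts at each time point. Present gene-expression changes by arm as well.
3. Label the Cycle 2, 4 and 6 blood samples as on drug. Label Month 12 blood and marrow as off drug, and describe that contrast as a persisting effect.
4. Keep the samples triggered by GVHD, toxicity or relapse, but report them separately and descriptively.
5. State whether Month 12 is counted from transplant or from first dose, in both calendars.

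The cost is document wording and a slightly larger model, with no added visit, biopsy or blood draw. The claim that marrow can support becomes narrower, and contrasts between 30 and 15 patients are imprecise (about ±0.62 standard deviations at best), so they should be reported as estimates with intervals.
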